8.6 Participant Withdrawal Criteria

Each participant has the right to withdraw from the trial at any time. The reason(s) for withdrawal will be recorded on the CRF if this is possible to do so. Although, there is no obligation for participants to provide a reason.

It is always within the remit of the physician responsible for a participant to withdraw a participant from a trial for appropriate medical reasons. Participants may be withdrawn from trial treatment for any of the following reasons as examples:

- 3 or more exacerbations/year
- Unacceptable adverse effects
- Development of serious disease preventing further treatment, or any change in the participant's condition that justifies discontinuation of trial treatment in the clinician's opinion
- Exacerbation in time period from randomisation to receipt of trial medication (home delivered from central pharmacy).

If participants are withdrawn from trial treatment or a participant wishes to stop trial treatment, they will be asked whether they would be willing to remain in scheduled trial follow-up, or if they do not want this, if they allow routinely collected clinical data (i.e. hospital admissions records and mortality) to be used for trial follow-up purposes.

If a participant decides to withdraw from the trial, any data already collected or results from tests already performed will continue to be used in the trial analysis unless explicitly requested by the participant for destruction. The participant should be asked if they would consent to routinely collected healthcare information (for example hospital admissions) to be used for trial purposes until the end of the trial.

8.7 Trial medication stopping rule/early discontinuation of trial treatment

Given the nature of the discontinuation interventions assessed in this trial, a trial treatment (IMP) stopping threshold has been set following discussion with patients and respiratory specialists. This does not affect a participant's right to withdraw from the trial at any time but has been established to gain important information on and off trial treatments for secondary outcomes analyses. The aim of this rule is to balance gaining important information about intervention effects of this trial (acute and long-term perspective of the discontinuations by secondary outcomes), versus the concern of leaving a patient who may have benefited from azithromycin, being on trial medication which may be placebo.

The trial medication stopping rule: participants will stop taking trial medication (IMP) if they have 3 or more exacerbations/year. They will stop IMP as soon as practically possible and can restart their regular azithromycin prescription if advised to by their clinical team.

This trial medication stopping rule does **not** affect the trial's primary endpoint. It is also noted that there is equipoise regarding azithromycin's effect on severe (hospitalised) exacerbations.⁵ In the COLUMBUS trial, which included a COPD population cohort similar to that recommended to consider azithromycin prevention treatment for in NICE guidelines, azithromycin reduced exacerbations from a baseline 4/year to 1.94 /year (95% confidence interval (CI) 1.50-2.52) vs placebo: 3.22/year (2.62-3.97).⁴³ Thus, three or more exacerbations/year seems a reasonable IMP stopping threshold, given the upper CI of exacerbation rates with azithromycin treatment and on discussion of this element of the protocol, was considered an acceptable threshold.

8.8 Treatment of COPD exacerbations and infections during the trial

Where participants need to have treatment for their COPD exacerbations or other infections in the trial, a trial card with information will explain that participants should be treated for their exacerbation or any other infections with non-macrolide antibiotics where at all possible. The trial medication can therefore then be continued during the treatment of the exacerbation/other infection which is in accordance with NICE guidelines¹ and does not require unblinding or temporarily stopping of the IMP.

However, if for any patient reason or it is deemed necessary by the treating clinical team or Principal Investigator that a macrolide antibiotic is required to treat the exacerbation or any infection (for example, patient allergies preclude an alternative class of antibiotics), then the IMP will be temporarily discontinued for the duration of exacerbation or infection treatment and restarted on completion of exacerbation/infection antibiotic treatment.

9 TRIAL TREATMENTS

This is a double-blinded, randomised, placebo-controlled trial comparing routine prescription of azithromycin chemoprophylaxis with placebo, or a combination of azithromycin in winter months (October-March), placebo in summer months (April-September).

The trial prescription will be matched as closely as possible to a participant's current regular prescription at time of trial enrolment (for example if an individual participant is on 250mg or 500mg thrice weekly then their trial prescription will match this). This is because the interventions being assessed in the trial are complete and seasonal discontinuations vs standard of care continued azithromycin treatment as per routine prescription at randomisation, rather than dose and frequency of azithromycin. This also enables the trial cohort to be inclusive of as many COPD participants on azithromycin rather than restricting to a particular dose/frequency treatment regimen.

Further information on trial treatments is provided in the pharmacy manual.

9.1 Treatment Summary

For the purpose of this trial, azithromycin and matching placebo are all considered as Investigational Medicinal Products (IMP)s conducted with a Clinical Trial Authorisation.

The trial is being carried out under a Clinical Trial Authorisation. The drug is therefore only to be used by the named investigators, for the participants specified in this protocol, and within the trial.

9.1.1 Azithromycin

Azithromycin, 250mg or 500mg film-coated tablets for oral administration.

Placebo will be manufactured by Eramol (UK) Limited to be identical in terms of appearance, taste and smell to azithromycin and will be dispensed in containers that are identical in appearance and labelling.

9.1.1.1 Legal status

Azithromycin is licensed for the treatment of certain infections. Although recommended as the drug of choice as a chemoprophylaxis indication to reduce the risk of COPD exacerbations in NICE, BTS and GOLD guidelines, and used as such in routine clinical care, azithromycin is not licensed specifically for this indication. Azithromycin will be used in this trial as indicated by its routine clinical care prescription.

9.1.1.2 Supply

The Sponsor will supply both active and placebo tablets for this trial and patients will switch from the standard commercial supply to the trial specific supply.

Given the double-blind nature of the trial, sufficient supply of azithromycin film-coated tablets (250mg and 500mg) will be sourced by Eramol (UK) Limited and matched placebo tablets (for both 250mg and 500mg) azithromycin will be made by Eramol (UK) Limited. Eramol will store stock of IMP and will send batches to the central pharmacy for the trial. The pharmacy will dispense IMP upon receipt of a secure notification via the study portal containing associated randomisation information. IMP will be sent by courier or Royal Mail to a participant's address.

9.1.1.3 Packing and Labelling

The Sponsor has entered into an agreement with Eramol (UK) Limited to supply packaged and labelled azithromycin 250mg and 500mg tablets and matched placebos for the purposes of the OPACE trial. The product will be provided in tamper proof bottles. Prior to release to central pharmacy, the supplier (Eramol (UK) Limited) will label bottles of azithromycin and placebo with annex 13 compliant labels; each bottle will be supplied with an unblinded tear-off portion of the label which will be removed at the point of dispensing by the pharmacy.

9.1.1.4 Storage conditions

Azithromycin tablets (250mg and 500mg) do not require any special storage conditions as per the SmPC.⁴⁴ They will be stored under ambient conditions.

9.1.1.5 Maximum duration of treatment of a participant

This is an event-driven trial, and the duration of follow-up and therefore potential maximum duration of trial treatment will be determined by monitoring of events and advice from the TSC regarding ongoing follow-up and continuation of the trial. It is anticipated that a participant may be on trial treatment for approximately 24 months. If a participant is recruited early in the trial and does not meet IMP stopping criteria, they may continue on trial treatment until the end of the whole trial. If a participant is recruited later on in the trial and does not meet IMP stopping criteria, they will have a shorter duration of treatment until the end of the whole trial.

9.1.1.6 Dose

Dose of azithromycin is as a participant's routine current standard of care prescription at time of enrolment (i.e. 250mg or 500mg). The frequency is as per a participant's standard of care prescription at the time of enrolment. This often is three times a

week. However, it is recognised some participants may have a different dosing regimen (i.e. 250mg daily) and the trial treatment prescription will match an individual's current prescription regimen as much as is possible. Azithromycin for prophylaxis to reduce COPD exacerbations will be a maximum dose of 250mg once daily.

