9.1.1.10 Dose modifications

No dose modifications will be undertaken during the trial. The dose will match the azithromycin prescription of routine clinical care at the time of trial enrolment.

9.1.1.11 Procedures for monitoring treatment compliance

The trial treatment (IMP) will be taken at home by participants. Compliance will be assessed by asking the participant to estimate their compliance. Participants will be asked to return any unused IMP and empty bottles to their local study site at trial visits.

9.1.1.12 Placebo comparator products

There will be one placebo, matched for 250mg azithromycin tablets, and one matched for 500mg tablets, matched in appearance, that will be identical in prescription, packaging, labelling, dosing and duration of treatment for azithromycin tablets.

The placebo tablets will contain microcrystalline cellulose, colloidal silicon dioxide, sodium starch glycolate and sodium stearyl fumarate.

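### The maximum dose in section 9.1.1.6 (250 mg once daily, unqualified) contradicts the 500 mg thrice-weekly regimen the trial is meant to match

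*Protocol*

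**What the plan says.** Section 9.1.1.6 (Dose) ties the dose to the participant's "routine current standard of care prescription at time of enrolment (i.e. 250mg or 500mg"). It says the frequency is often three times a week and recognises that "some participants may have a different dosing regimen (i.e. 250mg daily"). It then closes with the limit: "Azithromycin for prophylaxis to reduce COPD exacerbations will be a maximum dose of 250mg once daily".

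Other sections provide for 500 mg:

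- Section 9 says that "if an individual participant is on 250mg or 500mg thrice weekly then their trial prescription will match this".
- Section 9.1.1 names the trial product as "Azithromycin, 250mg or 500mg film-coated tablets for oral administration".
- Section 9.1.1.2 says that "sufficient supply of azithromycin film-coated tablets (250mg and 500mg) will be sourced", and section 9.1.1.3 records an agreement "to supply packaged and labelled azithromycin 250mg and 500mg tablets and matched placebos for the purposes of the OPACE trial".
- Section 9.1.1.12 provides a placebo matched to the 500 mg tablet as well as one matched to the 250 mg tablet.
- Section 9.1.1.10 rules out dose modification: "The dose will match the azithromycin prescription of routine clinical care at the time of trial enrolment".

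Section 8.3 adds that matching takes place within the dosing regimens the protocol specifies.

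**The concern.** A maximum dose is a treatment rule that sites and the central pharmacy act on. This one applies to azithromycin given to prevent COPD exacerbations, which is the indication of every participant: section 8.1 requires it and section 8.2 excludes prophylaxis for other conditions. Nothing in the protocol restricts the limit to daily regimens or describes it as a weekly total.

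For a participant on 500 mg thrice weekly, the limit and the matching rule cannot both be followed literally. A site could turn the participant away, halve the dose, or match the dose and appear to exceed the protocol's own maximum. Section 21 bars planned deviations and requires departures to be documented and reported, and about 135 primary and secondary care sites are planned (section 7.3), so different sites could settle the point differently.

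Halving the dose would matter most in the control arm, which is defined as continuation of the participant's existing regimen. Baseline azithromycin prescription is also a top-priority subgroup factor in section 15.1.2, so the permitted regimens should be unambiguous.

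**Working it through.** The check compares the stated limit with each regimen the protocol names, under each way the limit can be read.

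**Inputs**

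- Limit: 250 mg once daily (9.1.1.6).
- Named regimens: 250 mg thrice weekly and 500 mg thrice weekly (section 9); 250 mg daily (9.1.1.6).

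**Weekly totals** (dose × doses per week)

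- 250 mg thrice weekly: 250 × 3 = 750 mg
- 500 mg thrice weekly: 500 × 3 = 1500 mg
- 250 mg daily: 250 × 7 = 1750 mg

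**Reading A: literal, no more than 250 mg on any dosing day**

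- 250 mg thrice weekly and 250 mg daily are allowed; 500 mg thrice weekly is not. That is 2 of 3.
- Ratio of the 500 mg dose to the limit: 500 / 250 = 2.0.
- If the dose is cut to 250 mg with frequency unchanged: 250 × 3 = 750 mg/week, a reduction of (1500 − 750) / 1500 = 50%.

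**Reading B: a limit on daily regimens only**

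- 250 mg daily is at the limit, and the limit does not apply to the thrice-weekly regimens. That is 3 of 3.

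**Reading C: a weekly total of 250 × 7 = 1750 mg**

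- 750, 1500 and 1750 mg are all at or below 1750 mg. That is 3 of 3.
- 500 mg thrice weekly uses 1500 / 1750 = 86% of the limit.

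Readings B and C agree on the three named regimens but not on others. For example, 500 mg on alternate days is three doses one week and four the next: 500 × 3 = 1500 mg, then 500 × 4 = 2000 mg. Reading B does not address this regimen, while under reading C every second week exceeds 1750 mg. The text does not say which reading governs.

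Only reading A conflicts with section 9, the supply sections and section 9.1.1.10, but it is the reading the unqualified sentence gives.

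**The case against.** The strongest reply is that the intent is clear in context. The sentence gives a dose together with a frequency and comes directly after the mention of 250 mg daily, so it reads naturally as a limit on daily regimens. Section 9 names 500 mg thrice weekly and says it will be matched, and also says the trial does not want to restrict participants to one dose or frequency. Tablets and placebo are supplied at 500 mg, dose modification is ruled out, frequency follows routine care (9.1.1.7), and the eligibility criteria contain no dose limit. Section 8.3 arguably helps too, because 500 mg thrice weekly is a regimen the protocol specifies by name. A site would have to follow one loose sentence over several explicit ones to do harm. Dispensing detail sits in a pharmacy manual that is not available here, and the protocol does not say how many participants take 500 mg.

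Most of this stands. The intent can be inferred, the harm is possible rather than expected, and its frequency cannot be estimated. What does not stand is the suggestion that no correction is needed. The limit appears in the section headed Dose, where a prescriber would look first, and its meaning has to be reconstructed from other sections. The inference also leaves two candidate meanings that differ beyond the named examples.

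**Conclusion.** The concern holds as a defect in one sentence. As written, the maximum excludes one of the three regimens the protocol names, at twice the limit per dosing day; if enforced on a participant taking 500 mg thrice weekly, it would halve the weekly total. Under either likely intended reading all three regimens are allowed, so the dosing design itself is sound and only its statement is wrong.

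This is a minor correction, but one that should be made. It has no bearing on the sample size, the event target, the non-inferiority margin or the primary analysis method. The conclusion rests on the protocol's text alone. The number of participants affected is unknown, and the pharmacy manual may already handle the point correctly.

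**What to change.** Replace the last sentence of section 9.1.1.6 with a limit that covers both kinds of regimen, for example: *The maximum is 500 mg three times weekly or 250 mg once daily.* These values are inferred from the regimens the protocol names rather than from a stated maximum, so the sponsor's clinical team should confirm them, and should decide whether regimens such as 500 mg on alternate days are permitted.

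Optionally, let the mention of protocol dosing regimens in section 8.3 point to section 9.1.1.6, so that sites have one place to look.

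The cost is one sentence and, if wanted, one cross-reference. Eligibility, supply, visits, sample size, event target and analysis are unchanged.

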9.1.1.7 Administration

The frequency of administration and timing of each dose, will be matched to the participant's routine care prescription at the start of their trial participation. Azithromycin tablets are for oral administration only. Tablets can be taken with or without food. The tablets are recommended to be taken with approximately ½ glass of water and not within 2 hours of taking indigestion remedies.

9.1.1.8 Known drug reactions (undesirable effects)

The decision to start azithromycin therapy and the consideration of all potential clinical contraindications, cautions and interacting drugs should already have been considered by the original prescriber. These are listed as a reminder for the prescriber to ensure these are reviewed during the patient's ongoing care whilst in the trial.

The SmPC section 4.3 (Contraindications), section 4.4 (Special warnings and precautions for use), section 4.5 (Interaction with other medicinal products and other forms of interactions) and can be cross-referenced for further information.⁴⁵

Contraindications to azithromycin as per the SmPC, are hypersensitivity to azithromycin, erythromycin, any macrolide or ketolide antibiotic, or to any of the excipient listed in section 6.1 of the SmPC.

Potentially serious adverse effects which have occurred with azithromycin include hepatoxicity, pseudomembranous colitis, and clostridoides difficile-associated diarrhoea.

Prolonged cardiac repolarisation and QT interval, imparting a risk of developing cardiac arrhythmia and torsades de pointes, have been seen in treatment with macrolides including azithromycin, therefore co-administration with other products known to prolong QT should be undertaken with caution.

9.1.1.9 Interactions with other products and medicines

All interactions with current medication will have been considered by the original prescriber as part of standard of care prescribing. The below are listed as per the current SmPC but do not require additional monitoring throughout the trial other than what is mandated as part of standard of care.

- Antacids:
 - As per section 4.5 of the SmPC, in patients receiving both azithromycin and antacids, the medicinal products should not be taken simultaneously. Azithromycin must be taken at least 1 hour before or 2 hours after antacids.
- Digoxin and colchicine: Concomitant administration of macrolide antibiotics, including azithromycin, with P-glycoprotein substrates such as digoxin and colchicine, has been reported to result in increased serum levels of the P-glycoprotein substrate. Therefore, if azithromycin and P-gp substrates such as digoxin are administered concomitantly, the possibility of elevated serum concentrations of the substrate should be considered.

- Ergot derivatives: Due to the theoretical possibility of ergotism, the concurrent use of azithromycin with ergot derivatives is not recommended.
- Coumarin-Type oral coagulants: There have been reports received potentiated anticoagulation subsequent to co-administration of azithromycin and coumarin-type oral anticoagulants. Although a causal relationship has not been established, consideration should be given to the frequency of monitoring prothrombin time when azithromycin is used in patients receiving coumarin-type oral anticoagulants.
- Ciclosporin: Caution should be exercised before considering concurrent administration of these drugs. If co-administration of these drugs is necessary, cyclosporin levels should be monitored and the dose adjusted accordingly. Theophylline: As interactions of other macrolides with theophylline have been reported, alertness to signs that indicate a rise in theophylline levels is advised.
- Azithromycin should be used with caution in patients receiving medicines known to prolong the QT interval with potential to induce cardiac arrhythmia, e.g. hydroxychloroquine see SmPC for more details.

9.1.1.10 Dose modifications

No dose modifications will be undertaken during the trial. The dose will match the azithromycin prescription of routine clinical care at the time of trial enrolment.

9.1.1.11 Procedures for monitoring treatment compliance

The trial treatment (IMP) will be taken at home by participants. Compliance will be assessed by asking the participant to estimate their compliance. Participants will be asked to return any unused IMP and empty bottles to their local study site at trial visits.

9.1.1.12 Placebo comparator products

There will be one placebo, matched for 250mg azithromycin tablets, and one matched for 500mg tablets, matched in appearance, that will be identical in prescription, packaging, labelling, dosing and duration of treatment for azithromycin tablets.

The placebo tablets will contain microcrystalline cellulose, colloidal silicon dioxide, sodium starch glycolate and sodium stearyl fumarate.

9.2 Non Investigational Medicinal Products

No non-investigational medicinal products will be used in this trial. During follow-up, participants should continue to take any prescribed existing concomitant medication, and any new medication prescribed for them but these are not supplied to the participant within this protocol.

9.3 Concomitant Therapy

Any concomitant therapy clinically required will be permitted. However, participants should be instructed to take note of the interactions with other medicines stated within section 9.1.1.9 if they are on those medications.

9.4 Accountability and Dispensing

9.4.1 Pharmacy responsibilities

Please refer to the pharmacy manual for more information. A central pharmacy will be used who will be contracted by the Sponsor to provide storage, dispensing and accountability, and distribution of the IMP to participants. Responsibilities of the central pharmacy will be outlined in a study specific Technical Agreement.

9.4.2 Drug accountability

An agreement between the Sponsor, Eramol (UK) Limited, and Sponsor and the Central Pharmacy will be signed outlining any processes associated with drug accountability. Please refer to the pharmacy manual for more information.

9.4.3 Returns and destruction

Participants will be advised to return IMPs to local trial sites and the IMPs will be destroyed locally according to clinical care SOPs. No returns to the central pharmacy will be made. Please refer to the pharmacy manual for more information.

10 PROCEDURES AND ASSESSMENTS

Detailed information related to this section of the protocol are outlined in the sub-sections 10.1 to 10.6 below, and provided in the TPM.

